4.2 Non-Clinical Pharmacology

Ruxolitinib has high aqueous solubility and high permeability *in vitro* based on Caco-2 cell culture study. In single oral dose PK studies, ruxolitinib was absorbed rapidly with mean T_{max} values ranging from 0.5 to 2 h. In mice, dogs, minipigs and humans, there were minimal gender differences in the exposure of ruxolitinib and its metabolites. In rats, the C_{max} and AUC (area under the concentration-time curve) values were several-fold higher in females compared to males, due to metabolism by male rat specific isozymes 2C11, 2C13 and CYP3A2. The terminal half-life, routes and rate of excretion for ruxolitinib-derived radioactivity and metabolites observed between male and female rats were similar. The oral bioavailability was variable across species, ranging from 22% in male monkeys to virtually complete in female rats consistent with the species dependent clearance observed following IV dosing.

Following IV administration of ruxolitinib, the plasma clearance was species-dependent and ranged from moderate in male dogs (0.48 L/h/kg) to very high in male rats (9.4 L/h/kg). Based on the apparent steady-state volume of distribution, ruxolitinib was not distributed extensively beyond body water in dogs (1.1 L/kg) and monkeys (0.81 L/kg), but may be distributed to a greater degree in rats (1.6-3.8 L/kg) and minipigs (6.4 L/kg). The terminal elimination half-life ranged from 0.4 h (rat) to 2.5 h (dog). In monkeys, the PK parameters of ruxolitinib were comparable with and without the pretreatment of agents that increase gastric pH, indicating that elevated gastric pH is not likely to affect the oral exposure of ruxolitinib.

4.3 Animal Toxicity

Ruxolitinib was evaluated in several in animal based toxicology studies and did not exhibit significant toxicities at target concentrations. Cardiovascular evaluation in dogs demonstrated lowered blood pressure and increased heart rate at the highest dose of ruxolitinib (30 mg/kg). Effects noted in multiple-dose toxicity studies in mice (up to 4 weeks), rats (up to 6 months), and dogs (up to 12 months) were primarily those associated with the mechanism of action of ruxolitinib, a potent and reversible inhibitor of JAK-STAT signaling. Decreases in red blood cells, reticulocytes, eosinophils and lymphocytes have been observed along with lymphoid depletion in bone marrow and lymphoid organs. In addition, in dogs, demodectic mange, bacterial pneumonia and viral-induced papillomas, expected consequences of the pharmacology of JAK inhibition, were noted.

Embyro-fetal assessments in rat and rabbit, maternal toxicity and minimal embryo-fetal toxicity were noted at the highest doses. No teratogenicity was noted in rat or rabbit animal models.

There were no reported effects on fertility or early embryonic development. In an evaluation of fertility and early embryonic development, no effects were noted on reproductive performance or fertility in male or female rats. Increases in post-implantation loss were noted at the higher doses. In a pre- and post-natal development and maternal function study in rats there were no adverse findings for fertility indices or for maternal and embryo-fetal survival, growth, and developmental parameters. Ruxolitinib passed into the milk of lactating rats with an exposure that was 13-fold higher than maternal plasma exposure.

4.4 Absorption, bioavailability, and pharmacokinetics

Ruxolitinib is a potent and selective inhibitor of the JAKs with selectivity for JAK1 and JAK2 (Quintás-Cardama et al, 2010). Ruxolitinib potently inhibits JAK1 and JAK2 (IC₅₀<5nM), yet it does not significantly inhibit a broad panel of 28 kinases (<30% inhibition) when tested at 200 nM (approximately 100 × the average IC₅₀ value for JAK1 and JAK2 enzyme inhibition). In cell-based assays relevant to the pathogenesis of MPNs (myeloproliferative neoplasms), such as JAK/STAT signaling and the growth of cytokine-dependent tumor cell lines, ruxolitinib demonstrates IC₅₀ values of 80-300 nM. This effect is not due to general cytotoxicity, because ruxolitinib (up to 25 μ M) had no significant effect on the growth of a cytokine-independent, BCR-ABL-driven cell line. In addition, ruxolitinib inhibited JAK/STAT signaling and growth of a cell line expressing the constitutively active JAK2 mutant (JAK2V617F) that has been implicated in the pathogenesis of the majority of Philadelphia chromosome negative MPNs. Ruxolitinib was also tested in cell-based assays relevant to the increased inflammatory cytokine levels observed in MPNs that contribute to MPN-related systemic symptoms. Ruxolitinib potently inhibited IL-23 stimulated IL-22 production in human T cells (IC₅₀=50 nM), as well as IL-6, GM-CSF and TPO induced STAT3 phosphorylation in human peripheral blood mononuclear cells with IC₅₀ values < 100 nM.

Ruxolitinib also inhibited GCSF stimulated STAT3 phosphorylation in human neutrophils (IC₅₀=28 \pm 9 nM), as well as TPO induced STAT3 phosphorylation in human whole blood (IC₅₀=281 \pm 62 nM). Finally, ruxolitinib inhibited the production of IL-17 in response to IL-23 in T cells, and the production of monocyte chemotactic protein-1 in response to IL-6 in peripheral blood mononuclear cells with IC₅₀ values of \leq 120 nM (Fridman et al, 2011).

Ruxolitinib inhibited splenomegaly in mice resulting from intravenous (IV) inoculation of cells expressing the clinically relevant JAK2V617F mutation (Quintás-Cardama et al, 2010). After 3 weeks of treatment, more than 90% of vehicle-treated mice had succumbed to disease while more than 90% of ruxolitinib -treated mice survived. Treatment with ruxolitinib also reduced inflammatory

cytokine levels in these mice. The effects of ruxolitinib were also tested in a mouse disease model of polycythemia vera-like disease, based on transplantation of a 1:1 ratio of JAK2 wild type green fluorescent protein (GFP)-expressing murine bone marrow cells with JAK2V617F-positive murine bone marrow cells, which have a repopulation advantage. In this model, oral ruxolitinib treatment at doses of 30 or 90 mg/kg twice a day for 21 consecutive days reduced levels of phosphorylated STAT5 (pSTAT5) in the spleen, as well as the spleen size. Ruxolitinib also effectively reduced the red cell parameters (RBC count, Hgb, Hct and reticulocyte count) and neutrophil count. The treatment was well tolerated as assessed by monitoring body weight, and histological assessments of spleen and bone marrow samples post-therapy revealed a decrease of hypercellularity (erythroid and myeloid lineages) in ruxolitinib treated groups as compared to vehicle treated animals. However, no significant decrease in the mutant allele burden surrogate readout (percentage of GFP-negative cells, i.e. cells expressing JAK2V617F) was observed, as assessed by flow cytometry. Treatment of mice with ruxolitinib in a cytokine-dependent multiple myeloma (MM) xenograft model resulted in a dose-dependent suppression of phosphorylated STAT3 (pSTAT3) and tumor growth. Efficacy was also observed in additional preclinical tumor models representing both hematologic and solid tumors. Taken together, these data indicate that ruxolitinib will be able to inhibit wild-type and mutant JAKs in the clinical setting and are consistent with its observed efficacy in patients with MPNs.

4.5 Clinical Trials

To date, more than 9,400 patients have received ruxolitinib in Novartis and Incyte sponsored interventional clinical trials. The clinical experience of ruxolitinib in humans is mainly based on data obtained in patients with myelofibrosis (MF), polycythemia vera (PV), and graft versus host disease (GVHD). Limited data are available in healthy volunteers, essential thrombocytosis, multiple myeloma, prostate cancer, pancreatic cancer, thalassemia and rheumatoid arthritis.

The clinical database (safety set) in solid tumor and hematologic malignancies consists of 787 patients treated in 6 studies evaluating patients with myelofibrosis (MF) (n=679), prostate cancer (n=22), MM (n=13), essential thrombocythemia (ET), and polycythemia vera (PV) (n=73), of whom 617 patients received ruxolitinib. Hematologic events are the most frequently reported adverse events (AEs) and include thrombocytopenia and anemia. The majority of these AEs are of Grades 1-2, seldom led to study drug discontinuation (<1% of patients), and can be usually managed through dose reduction or interruption. Increased rates of anemia resulted in an increase in packed red blood cell (PRBC) transfusion requirements for some ruxolitinib-treated patients. Platelet transfusions while on ruxolitinib were rare. Biochemistry laboratory abnormalities of alanine aminotransferase (ALT), aspartate aminotransferase (AST) and cholesterol were reported. The majority of these increases were Grade 1 or 2. No Grade 4 events were reported.

Safety in clinical pharmacology studies

The safety profile for ruxolitinib in the Phase I development program was assessed in over 145 healthy subjects for single doses from 5 mg to 200 mg, and in 53 healthy subjects for repeat doses from 15 mg to 50 mg b.i.d. and 50 to 100 mg q.d. Ruxolitinib has also been administered to 32 subjects with various degrees of renal impairment, 24 subjects with various degrees of hepatic impairment, and 50 subjects with RA (rheumatoid arthritis). AEs were, in general, mild and resolved without interventions. In the first in human study one subject had hyponatremia after receiving 5 mg ruxolitinib. The hyponatremia was assessed as severe in intensity, unrelated

to study medication, reversed within 5 days, and was reported as a serious adverse event (SAE). A Phase I dose escalation study and a study to evaluate food effect in Japanese healthy volunteers showed that administration of ruxolitinib with a high-fat meal led to results that were in line with results from the North American study. A Phase I dose escalation study in Chinese healthy volunteers showed similar overall results over a dose range of 10-50 mg. The pharmacokinetics of ruxolitinib was linear in the dose range studied, with a short half-life of 2-4 hours resulting in no notable drug accumulation following multiple doses.

In the repeat-dose study in healthy subjects, the intensity of an adverse event was graded according to the protocol-defined toxicity criteria based on Rheumatology Common Toxicity Criteria V 1.0. The dose-limiting AE was neutropenia, which occurred at a dose of 50 mg b.i.d. Neutropenia as an AE was noted in three subjects, all receiving the highest dose of ruxolitinib, 50 mg b.i.d. Neutropenia at the Grade 4 level, assessed as severe, led to study drug discontinuation on Day 5 in one subject, and was reported as a SAE. Neutrophil count returned to a normal level 12 days after the final dose of study medication. In two other subjects, neutropenia was Grade 1 or 2, and resolved with dose interruption or during continued dosing. The AE profile was similar for single- and multiple-dose studies, and no differences were observed between males and females. The most frequent (≥ 2 subjects) treatment-emergent AEs (TEAEs) occurring in the Phase I multiple-dose study were: neutropenia (4.2%), dizziness (2.8%), headache (2.8%) and nausea (2.8%). Overall, in healthy volunteer studies where frequent sampling of the neutrophil count was performed, a transient, reversible decrease in neutrophil count was frequently seen following dosing, which reversed after 12-24 hours off drug. Two clinical pharmacology studies are ongoing to evaluate the effect of ruxolitinib on the pharmacokinetics of orally administered midazolam in healthy males subjects and of monophasic oral contraceptives in health female subjects.

The first Periodic Safety Update Report (PSUR) for ruxolitinib covered the reporting period from 16 Nov 2011 to 22 Feb 2013. A critical analysis of the efficacy and safety data revealed that the overall benefit-risk assessment of ruxolitinib remains favorable. Based on a single confirmed case of PML in an MF patient treated with ruxolitinib, this condition has been identified as an important potential risk. Reports of tuberculosis continue to be received in ruxolitinib-treated subjects in clinical trials. While the cumulative incidence of these tuberculosis reports appears to decline since the original Phase III trials, given the potential impact of JAK1/JAK2 inhibition upon immune defense, the risk tuberculosis will be monitored closely in subsequent PSURs.

Phase III studies in patients with myelofibrosis

The Controlled Myelofibrosis Study with Oral JAK Inhibitor Treatment I, (COMFORT-I) was a randomized, double-blind, placebo-controlled, multicenter study comparing the efficacy and safety of ruxolitinib tablets to a matched placebo in 309 patients with MF. The primary objective was to evaluate the efficacy, safety and tolerability of ruxolitinib given b.i.d. compared to placebo in patients with MF. Patients were randomized in a 1:1 ratio of ruxolitinib: placebo with no stratification. Ruxolitinib starting dose was based on baseline platelet count as follows: patients with baseline platelet count $> 200 \times 10^9/L$ started at 20 mg b.i.d. and patients with baseline platelet count $> 100 \times 10^9/L$ to $\leq 200 \times 10^9/L$ started at 15 mg b.i.d. The primary endpoint for this study was the percentage of patients with $\geq 35\%$ reduction in spleen volume

assessed by imaging (MRI or CT) from baseline, at Week 24. The Controlled Myelofibrosis Study with Oral JAK Inhibitor Treatment II (COMFORT II) was an open-label, randomized, active-comparator, multicenter study comparing the efficacy and safety of ruxolitinib tablets versus best available therapy as selected by the investigators in 219 adults patients with myelofibrosis. Key eligibility criteria were as follows: adult MF patients, not candidates for stem cell transplantation, with two or more risk factors identified by IPSS, palpable spleen length \geq 5 cm below the left costal margin, peripheral blast count $<$ 10%. The primary endpoint for this study was the percentage of patients with \geq 35% reduction in spleen volume assessed by imaging (MRI or CT) from baseline, at Week 48. These trials identified statistically significantly larger proportion of patients randomized to ruxolitinib achieved a \geq 35% reduction from baseline in spleen volume compared to patients randomized to control. This effect was seen at both Week 24 (primary endpoint in COMFORT-I) and Week 48 (primary endpoint in COMFORT-II). For patients who remained on study, the median percent reduction from baseline in spleen volume in both ruxolitinib arms was approximately 30%, was reached as early as Week 12 and was maintained throughout the study. The control arms had a median percent increase from baseline in spleen volume throughout the study.

Phase III studies in patients with polycythemia vera

The RESPONSE Trial was a global, randomized, open label phase III pivotal study comparing ruxolitinib (starting dose of 10 mg b.i.d.) with best available therapy (HU, pipobroman, immunomodulatory drugs, pegylated interferon or interferon, anagrelide, observation only) in PV patients. The protocol was designed for patients with evidence of need for phlebotomy and splenomegaly, either resistant or intolerant to HU. The primary endpoint was a composite one with phlebotomy control (absence of phlebotomy from Week 8 to 32) and reduction in spleen volume by MRI (or CT if MRI is clinically contraindicated) of at least 35% measured at 32 weeks. Two key secondary endpoints included durability of the primary endpoint and complete hematologic remission. The primary efficacy objective was based on a composite endpoint consisting of Hct control (absence of phlebotomy eligibility) and of at least 35% spleen volume reduction as assessed by central radiologic evaluation. Significantly more patients randomized to ruxolitinib met the primary endpoint at Week 32 when compared to patients randomized to BAT, 22.7% vs. 0.9%, respectively ($p < 0.0001$). Significantly more patients randomized to ruxolitinib maintained primary response (Hct control and spleen volume reduction) at Week 48 when compared to patients randomized to BAT, 20.0% vs. 0.9%, respectively, ($p < 0.0001$). Among the 25 patients randomized to ruxolitinib who had achieved primary response (Hct control and \geq 35% reduction in spleen volume), 23 maintained the response through data cutoff (15-Jan-2014). The probability of maintaining primary response for 48 weeks and longer after the start of response was 0.90. Longer follow-up to Week 80 showed that no further patients had lost the primary response.

Ruxolitinib for the treatment of inadequately controlled PV without splenomegaly (RESPONSE-2) followed the pivotal RESPONSE study which demonstrated that ruxolitinib was superior to BAT at controlling Hct and improving splenomegaly and symptoms in PV patients with splenomegaly who were inadequately controlled with HU. In the RESPONSE-2 study, the efficacy and safety of ruxolitinib was assessed in controlling disease in patients with PV without splenomegaly who need second-line therapy. The primary endpoint was the proportion of patients

achieving Hct control at week 28. Analyses were done according to an intention-to-treat principle, including data from all patients randomly assigned to treatment. Hct control was durable for a higher proportion of patients in the ruxolitinib arm compared to the BAT arm at Week 52 (59.5% vs 6.7%, respectively) and at Week 80 (47.3% vs 2.7%, respectively). The median duration of Hct control was not achieved in the ruxolitinib and the BAT arm. The estimated proportion of patients without an event at 72 weeks was 80.7% in the ruxolitinib arm. The proportion of patients without event at 72 weeks in the BAT arm was not reported due to very small number of patients responding to BAT. CHR was durable for a higher proportion of patients in the ruxolitinib arm compared to the BAT arm at Week 52 (23.0% vs 4.0%, respectively) and at Week 80 (24.3% vs 2.7%, respectively). In the ruxolitinib arm, the median duration of CHR was 34.0 weeks. The median duration of CHR in the BAT arm was not reported due to very small number of patients responding to BAT.

Phase I/II study in patients with prostate cancer

A Phase II, open label study of ruxolitinib administered orally to patients with androgen independent metastatic prostate cancer (AIPC) was performed. The primary endpoint was PSA50 (prostate-specific antigen) response rate, a clinically validated endpoint associated with clinical benefit in patients with metastatic prostate cancer. This endpoint is defined as a PSA decline from baseline of 50% or greater, confirmed by measurement on two occasions at least 4 weeks apart. The study used a Simon 2-stage optimal design. The first stage of the trial (Part 1) was designed to enroll 21 patients. If fewer than two PSA50 responses were observed in the first 21 patients (no later than 10 weeks after the last patient in the first stage is enrolled), the trial would be closed and the agent will be declared inactive as a monotherapy. If two or more PSA50 responses are seen in the first stage, an additional 20 patients would be enrolled in the second stage (Part 2) for a total of 41 patients. The study in patients with advanced prostate cancer completed enrollment of 22 subjects in the first stage of the study. The study endpoint permitting advancement to a second stage of the study was not reached. Seventeen of 22 subjects enrolled experienced death or protocol-defined progressive disease while on study.

Given that all patients discontinued the study due to protocol-specified lack of efficacy, the primary efficacy endpoint of PSA50 response rate was not assessed. Similarly, the secondary endpoints of median time to progression and tumor response rates were not assessed. All patients provided samples for the secondary endpoints of evaluating population PK and plasma PD markers; however, the samples were not assessed as part of this analysis.

The primary endpoint of safety and tolerability was assessed in this analysis. All patients experienced at least one TEAE, and the majority of patients (16 patients; 72.7%) experienced treatment-related TEAEs. The events associated with ruxolitinib treatment included anemia, fatigue, diarrhea, nausea, leukopenia and peripheral edema, all of which were not unexpected events in this patient population of metastatic androgen AIPC, as were the most frequently reported severe or life-threatening TEAEs (anemia, thrombocytopenia, peripheral edema, increased blood alkaline phosphatase, bone pain).

Treatment with ruxolitinib was generally well-tolerated. Among the 11 SAEs reported by nine patients, the only SAE that was reported by more than one patient was anemia (two patients), and

only two SAEs were considered to be possibly or definitely related to study medication by the investigator (cardiac arrest and anemia, respectively). Further, only one patient discontinued treatment as a result of an AE (anemia). Among the four deaths, cardiac arrest was deemed by the investigator as possibly related to study medication in one patient, but the patient had other risk factors that may have also contributed to the event; the other three deaths were likely associated with medical history and metastatic AIPC.

Eight patients had laboratory abnormalities that resulted in serious, severe, or life-threatening AEs, which included the following events: anemia, increased blood alkaline phosphatase, increased γGT, thrombocytopenia, hyperuricemia, and leukopenia. There was no specific trend among patients with regards to laboratory abnormalities or ECG values out of the normal range. Overall, there were no specific safety concerns associated with ruxolitinib.

4.6 Other Agent(s)

Not applicable

5. STUDY DESIGN

5.1 General Design

This is an open-label, multi-center, Phase II study to evaluate the efficacy of ruxolitinib in post-transplant patients with advanced cutaneous squamous cell carcinoma.

Study Intervention: In a safety lead-in of 6 patients, subjects will receive ruxolitinib 15mg BID. After 4 weeks, if dose-limiting toxicities (DLT) are observed in 1 or fewer patients, the study will enter stage 1 of the Simon two-stage design where all subsequent patients will receive a starting dose of ruxolitinib 15mg BID. If more than 1 DLTs are observed, another cohort of 6 patients will be treated at a dose of 10mg BID. If less than 2 DLTs are observed at the new dose of 10mg, then the study will proceed to stage I using this dose; otherwise the study will stop.

Individual subjects may have dose reductions of ruxolitinib during the course of treatment, based upon safety laboratory assessments.

Schedule of Evaluations: Subjects will have regularly scheduled study visits at the clinical site on Day 1 and Day 15 (\pm 3 days) of the first cycle, then on Day 1 (\pm 3 days) of every subsequent cycle (starting cycle 2), where safety assessments, including laboratory assessments, vital signs, and physical examinations will be performed (see Section 12 for study calendar).

Response to treatment will be determined by CT scans of the chest, abdomen, and pelvis with contrast. The overall response rate for the primary endpoint evaluation will be determined by RECIST v1.1 criteria. In patients who are unable to get a CT scan w/ contrast due to renal function (or any other reason), an MRI with and without contrast may be used instead. Imaging will be performed at the following time points:

| | |
|--------------------------------------|---|
| Baseline scan | Baseline scan within 4 weeks prior to first treatment |
| Weeks 1 – 32 | Every 8 weeks +/- 1 week (at weeks 8, 16, 24, 32) |
| Weeks 33 – until disease progression | Every 12 weeks +/- 1 week (at weeks 44, 56, 68, 80, 92, 104) |
| 2 years | If subjects achieve ongoing disease control at 2 years, patients will be continued on study treatment and observed with imaging every 12 weeks +/- 2 weeks. |

Duration of treatment: Subjects will continue treatment until confirmed radiographic disease progression, intolerable toxicity or side effects (Section 6.5.1).

Correlative studies: A minimum of 10 enrolled subjects must undergo paired biopsies for correlative studies. CT-guided biopsies will be collected at baseline and between C2D1 and C2D8 of therapy for correlative studies. A biopsy at the time of disease progression is optional in all subjects. Subjects in whom a biopsy is technically not feasible or in whom would result in unacceptable risk, in the opinion of the investigator, may be exempted from the biopsy requirement with discussion with the principal investigator.

Whole blood will be requested as outlined in section 13.2 for peripheral blood mononuclear cell (PBMC) and circulating tumor DNA (ctDNA) collection to evaluate the effect of ruxolitinib on circulating immune cell populations before and during treatment and to further evaluate ctDNA as a potential biomarker of disease response.

Duration of follow-up: Adverse events and laboratory tests will be graded using the NCI CTCAE v5.0 scoring system. Adverse events will be assessed continuously during the study and for **90 days** after the last dose of treatment. Subjects will be followed for at least **90 days** post-study, or until all treatment related adverse events have recovered to baseline or are deemed irreversible by the investigator. Subjects who are removed from study for reasons other than progression of disease will be followed every 3 months with imaging to evaluate disease status and survival analysis while the study remains open.

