5.2 Number of Patients

Utilizing a Simon Two-Stage Mini-Max design, 18 patients with advanced cSCC will be accrued in the first stage. If 1 or more patients achieve a response, then an additional 14 will be accrued. If 3 or fewer responses are seen, the study will be declared negative. If the initial safety lead-in does not result in advancement to stage I, an additional 6 patients will need to be accrued for a second safety lead-in. Assuming a 10% drop-out rate, we anticipate a total accrual of 35 patients with a maximum potential accrual of 41 patients (see Statistical Considerations).

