5.3 Correlative Studies

5.3.1 Tumor biopsies for pharmacodynamic assessment

The biological activity of ruxolitinib will be assessed by performing paired tumor biopsies

at baseline, and between Cycle 2 Day 1 and Cycle 2, Day 8 of study therapy. These biopsies will be mandatory in the first 10 patients enrolled on Stage I of the study (first 18 enrolled subjects), and optional in subsequent patients. A biopsy at the time of disease progression is optional in all patients. (Note: If sufficient flash frozen tumor material is available from a prior tumor biopsy performed within 3 months of registration with no intervening therapy, then a repeat baseline biopsy will not be necessary.)

A goal of at least 3 cores and up to 8 cores from the patient's tumor biopsy specimen, if safe to obtain, will be obtained for research purposes. The first core will be placed in buffered formalin and paraffin-embedded as standard of care. Subsequent cores will be flash frozen.

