17. STATISTICAL CONSIDERATIONS

17.1 Study Design and Sample Size

This is a multi-center, non-randomized, open-label phase 2 trial to evaluate the efficacy and safety of ruxolitinib in post-transplant patients with advanced cutaneous squamous cell carcinoma. The primary endpoint is overall response rate, defined as the best response confirmed

within the 24 weeks of the start of study therapy.

We will use a Simon Two-Stage Min-Max design with a target overall response rate of 20% (alternative hypothesis), compared to a historical response rate of 5% (null hypothesis) with chemotherapy, with one-sided probability of a type I error set at 0.10 and power of 90%. In the first stage, 18 patients will be accrued. If less than 1 patient achieves a response among the initial 18 patients, the study will be declared negative and terminated. If at least 1 patient achieves a response, an additional 14 patients will be accrued to the second stage for a total of 32 evaluable patients. Overall, if 4 or fewer responses are seen, the study will be declared negative. If at least 5 total patients achieve a response, that treatment will be declared positive for attaining the primary endpoint. There is a 40% chance of stopping at Stage 1 if the true confirmed response rate is at most 5% (null hypothesis). Accounting for 10% dropout, we will plan to enroll a total of 35 patients unless a second safety lead-in is required, in which case the the maximum potential accrual will be 41 patients.

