17.2 Study Endpoints and Analytic Plan

All subjects who receive at least one dose of study drug will be considered evaluable and included in the efficacy and safety analysis.

Definition of primary outcome/endpoint:

The primary endpoint is the overall response rate defined as the best response within the first 24 weeks of the start of study therapy using RECIST v. 1.1 that has been confirmed at a subsequent time point (≥ 4 weeks).

Definition of secondary outcomes/endpoints:

PFS is defined as time from enrollment to time of clinical or radiographic disease progression as defined by RECIST v.1.1 criteria. OS is defined as time from enrollment to time of death from any cause.

Analytic plan for primary objective:

The overall response rate will be summarized using point estimates and 95% confidence intervals.

Analytic plan for secondary and exploratory objectives:

- We will estimate the survival distribution for both PFS and OS endpoints using the Kaplan Meier method. The log rank test will be used to examine differences between survival curves using prognostic markers.
- For correlative studies we will apply either the Fisher's exact test or Wilcoxon Rank Sum test to examine the associations between response status and changes in markers expression for categorical and continuous variables, respectively. Because of the limited sample size, the biomarker data analysis is for exploratory research only.
- Toxicity data will be summarized by type, frequency, and severity according to the NCI CTCAE criteria v4.0.

- Pharmacokinetic and pharmacodynamic parameters will be summarized using descriptive statistics and graphical methods (individual profile plots).

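### The plan does not say whether the six lead-in patients belong to Stage 1, and Section 17.2 would let extra patients into a decision rule built for 18 and 32

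*Combined protocol and SAP*

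**What the plan says.** **Where the lead-in sits.** Section 5.1 treats six patients, waits four weeks, and if the toxicity criterion is met "the study will enter stage 1 of the Simon two-stage design where all subsequent patients will receive a starting dose". Section 5.2 also treats passing the lead-in as the step that opens Stage I. Section 5.3.1, on biopsies, instead refers to "Stage I of the study (first 18 enrolled subjects", a count that takes in the first six patients. Section 17.1 states "In the first stage, 18 patients will be accrued", followed by 14 more for 32 evaluable, and does not say whether lead-in patients count.

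**Totals.** Section 17.1: "Accounting for 10% dropout, we will plan to enroll a total of 35 patients". Section 5.2: "we anticipate a total accrual of 35 patients with a maximum potential accrual of 41 patients", the larger figure applying if a second lead-in of six is needed.

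**Analysis set.** Section 17.2: "All subjects who receive at least one dose of study drug will be considered evaluable and included in the efficacy and safety analysis". It makes no exception for a lead-in cohort treated at a dose that is then dropped, and it does not limit the count to 32.

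**The concern.** A Simon rule is a set of integer cut-offs tied to two fixed sample sizes. Here the study stops on no response among 18, and the final success threshold is set for 32. If the text allows more patients into either count while the cut-offs stay put, the trial is less likely to stop early on an inactive drug and more likely to call it active. Six extra patients can arise in two ways: the lead-in taken as preceding Stage 1, as Section 5.1 reads, or a lead-in cohort at a dropped dose that Section 17.2 keeps in the efficacy analysis. In the second case the primary count would also mix doses. Separately, a site or analyst working from Section 5.1 would expect more patients than the stated accrual provides.

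**Working it through.** **Inputs.** From Section 17.1: "target overall response rate of 20% (alternative hypothesis), compared to a historical response rate of 5% (null hypothesis"), and "with one-sided probability of a type I error set at 0.10 and power of 90"%. Stage sizes are 18 and 14; stop if 0 of 18 respond. The final threshold is 5 or more responses in Section 17.1 and the synopsis, but 4 or more in Section 5.2, so both are carried through. The lead-in cohort is six, and dropout is 10%.

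**1. Formulas.** For stage-1 size n1, total n, success threshold c and response rate p:

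- Early stopping: (1 − p)^n1
- Probability of a positive trial: the sum over x = 1 to n1 of b(x; n1, p) × P[Bin(n − n1, p) ≥ c − x], where b is the binomial probability

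**2. The plan's own design.** An exhaustive minimax search with these inputs returns 18 and 32, stopping on 0 responses, with success at 4 or more. Early stopping at 5% is 0.95^18 = 0.397, matching the stated 40%.

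**3. Headcount under each reading.**

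| Reading | Needed for the rule | After 10% dropout | Plan states |
|---|---|---|---|
| Lead-in inside the 18 | 32 | 32/0.9 = 35.6 | 35 |
| Same, plus one cohort at a dropped dose | – | 35 + 6 = 41 | 41 |
| Lead-in before Stage 1 | 6 + 18 + 14 = 38 | 38/0.9 = 42.2, so 43 | not provided for |
| Same, with two lead-ins | 12 + 18 + 14 = 44 | 44/0.9 = 48.9, so 49 | not provided for |

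Only the first pair fits the stated totals. In the 41 case one cohort of six lies inside the 35 and the other outside it. The documents do not spell this out; it is inferred from the arithmetic.

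**4. Error rates.** If the six are wholly inside or wholly outside the 18/32, the test is the same and so are its properties. They move only if six extra patients are added to both counts, giving 24 then 38, with the cut-offs unchanged. Early stopping then becomes 0.95^24 = 0.292.

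| Counts | Success at | Early stop, p = 5% | Type I error | Power, p = 20% |
|---|---|---|---|---|
| 18 / 32 | ≥4 | 39.7% | 7.2% | 90.1% |
| 18 / 32 | ≥5 | 39.7% | 2.0% | 79.3% |
| 24 / 38 | ≥4 | 29.2% | 11.9% | 96.0% |
| 24 / 38 | ≥5 | 29.2% | 4.0% | 90.1% |

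**5. Dropout.** 35 × 0.9 = 31.5, just under 32. Enrolling 35 leaves room for 35 − 32 = 3 losses, and 3/35 = 8.6%.

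**The case against.** The best defence is that Section 17.1 already fixes the rule: it speaks of the initial 18 patients and of 32 evaluable in all. That wording, Section 5.3.1 and the totals all favour a lead-in inside Stage 1; only the sequencing language in Sections 5.1 and 5.2 points the other way. Section 17.2 defines an analysis set for a point estimate and confidence interval and does not restate the Simon rule, so 24/38 is not a design that the protocol adopts. All of this stands, and it limits the point. It does not remove it. No section says that the lead-in counts, and the all-dosed sentence covers efficacy with no exclusion for a dropped dose.

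Three stronger readings are tempting, and the documents do not support them:

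- A reader might infer that the clash between Sections 5.1 and 5.3.1 by itself leaves the error rates open. It does not, because either placement still gives an 18/32 test.
- A reader might apply the cut-offs to 24 then 41 patients. That needs the three dropout-allowance patients counted as analysed and all placed in Stage 2, which no section says.
- A reader might compute the chance that 35 enrolled yield 32 evaluable under 10% dropout and call the trial under-enrolled. Under Section 17.2 a patient who drops out after one dose is still evaluable, so that probability contradicts the plan's own rule. The dropout point is one patient of rounding.

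**Conclusion.** The point holds as a conflict of wording with a conditional statistical consequence. The placement of the lead-in is contradictory, and the totals can be met on only one reading. The 18/32 operating characteristics change only if the all-dosed rule of Section 17.2 is carried into the go/no-go count.

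The size given assumes exactly six extra patients in both the interim and final counts, independent responses, and the same response rate in those six as in the rest. On that basis early stopping under the null drops by about 10 percentage points (39.7% to 29.2%). Type I error goes to 11.9% or 4.0%, depending on the cut-off, and only the first breaks the 10% limit. That the plan contains two cut-offs is a separate issue, to be reconciled on its own; nothing here depends on which is kept.

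**What to change.** - **Sections 5.1, 5.2 and 17.1:** state that lead-in patients treated at the dose carried forward are the first six of the 18 Stage 1 patients. This agrees with Section 5.3.1 and with the totals of 35 and 41. Add to Section 5.3.1 that the 18 are those at the dose carried forward, since after a second lead-in the first 18 enrolled would include the dropped-dose cohort.
- **Section 17.2:** state that the Simon decision uses exactly the first 18 and first 32 evaluable patients at that dose. Patients at a dose not carried forward stay in the safety analysis and have their responses reported separately. Without this amendment the other edits would contradict the all-dosed sentence. Say which meaning of evaluable applies, because Sections 15.2 and 17.5.2 define the response population differently.
- **Dropout:** restate the allowance as 3 of 35 (8.6%). Alternatively, keep 10% and change the totals to 36 and 42.

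The cost is protocol wording in a few sections. The decision sample sizes do not change, and accrual changes by at most one patient. If the sponsor instead wants the lead-in to stand outside Stage 1, that is workable, but the totals must then rise to about 43 and 49.
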